## Study Intervention

1. This study has only one arm and all participants will receive Cholecalciferol (vitamin D3) 5,000 IU and calcium citrate 1000 mg daily for 12 weeks. There will be no placebo and no blinding of the agent. Participants will receive a 3 month supply of drugs administered by the Loyola pharmacy. Serum vitamin D and calcium levels will be measured at study initiation and at 6 and 12 weeks (study end). We will stop both vitamin D and calcium supplementation in participants with serum calcium levels  $\geq 10.6$  meq/L and/or a 25(OH)D level  $\geq 80$  ng/dl at the 6 week visit. These participants will continue to be monitored in the study but they will not receive any drugs. The vitamin D will be obtained from Biotech Pharmacal, Inc. Calcium citrate 1000 mg tablets will be obtained from Walgreens. The Loyola pharmacy will dispense all supplements.

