For participants who do enroll in the BBC and Vitamin D study, a serum specimen (15 ml) will be collected at the 6-week follow-up visit to measure serum calcium and 25(OH)D. Serum calcium and 25(OH)D will be measured at the Quest lab.

At the 12 week visit, 15 ml of blood will be obtained to again measure 25(OH)D, 1,25(OH)2D and PTH levels and serum calcium. Vitamin D measures, serum calcium and PTH will be measured by Quest. Participants will also be asked to collect a 24-hour urine collection to measure urinary calcium excretion. Urine calcium excretion will be measured by Quest.

Participants will receive a copy of all laboratory test results via letter. A data safety monitoring board will review all adverse events and laboratory data at 6 weeks to ensure safety of all participants. Participants will be provided a copy of all laboratory tests. Participants will be instructed to share these test results with their physician. If needed, [name] will identify a primary care physician for the participant if the participant does not have a primary care doctor.

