### Inclusion Criteria

1. Age 25-45 years
2. Self-reported race/ethnicity African American
3. BMI  $\geq$  25 kg/m^2
4. Total 25(OH)D levels  $<$  20 ng/ml (50 nmol/L)
5. No use of vitamin D supplements within past 30 days of the screening visit
6. Able to provide written informed consent
7. Willing to take a vitamin D supplement daily for 12 weeks
8. Willing to return for follow-up visits to measure blood pressure and provide a blood sample to measure vitamin D and serum calcium
9. No current use of blood pressure lowering medications
10. Systolic blood pressure  $\geq$  120 mmHg and diastolic blood pressure  $\geq$  60 mmHg
11. Estimated calcium intake  $<$  1000 mg/day

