## Exclusion Criteria

1. Medical history of chronic disease that affect gastrointestinal absorption of vitamin D: Crohn's disease, cystic fibrosis, and celiac disease
2. Use of medications which may affect total 25(OH)D levels: antiepileptic drugs, steroids, bile acid sequestrants, lipase inhibitors, orlistat
3. Current use of vitamin D supplements or use in past 8 weeks and unwillingness to discontinue for at least 1 month prior to study enrollment
4. History of kidney stones or hypercalciuria ( > 250 mg urinary calcium excretion)
5. Fasting serum calcium  $\geq$  10.2 mg/dl at the screening visit
6. Average systolic blood pressure  $\geq$  140 mmHg
7. Average diastolic blood pressure  $\geq$  90 mmHg
8. Presence of active malignancy, active thyroid disease or sarcoidosis
9. Pregnant or planning a pregnancy or breastfeeding
10. Estimated glomerular filtration rate (based on serum creatinine level) is < 60 ml/min/1.73 m^2 based on the Modification of Diet in Renal Disease formula
11. Enrolled in a clinical trial
12. Any history of a heart attack, stroke, angioplasty or coronary artery bypass grafting or physician diagnosis of heart failure

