### c. Sample size determination

This pilot study will collect data to design a larger randomized clinical trial. The sample size of 15 participants will allow us to detect adverse events which occur at a rate  $\geq$  20% with 96% probability. We will have a 79% probability of detecting complication rates  $\geq$  10%. We will have moderate probability to detect adverse events which occur in 5% or less of participants. As a small pilot study, we will determine the tolerability of taking 5,000 IU of Cholecalciferol with 1000 mg elemental calcium daily for 12 weeks and will examine changes in measures of vitamin D status including total 25(OH)D, free 25(OH)D levels and PTH levels.

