**G6. SAFETY AND ADVERSE EVENTS**

**a. Safety Monitoring**

We will query any hospitalizations or emergency room visits over the past month and reasons for those visits at the baseline, 6 and 12 week follow-up visits. Serum calcium and vitamin D levels will be measured at 6 and 12 weeks and anyone with serum calcium levels  $\geq 10.6$  meq/L and/or a 25(OH)D level  $\geq 80$  ng/ml or symptoms of vitamin D intoxication (e.g. bone pain, nausea, vomiting) will stop treatment. All adverse events will be reported to the Loyola University Chicago Health Sciences Institutional Review Board. The dose of vitamin D3

(5,000IU) is 1000 IU lower than the recommended dose for treating adults with 25(OH)D levels < 20 ng/ml. We will also exclude individuals with calcium intake that is at or above the current recommended daily calcium intake (1000 mg).

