### Stopping plans

Any participant who develops a serum calcium levels  $\geq 10.6$  meq/L and/or a 25(OH)D level  $\geq 80$  ng/ml or symptoms of vitamin D intoxication (e.g. bone pain, nausea or vomiting) will stop treatment but they will continue to be monitored in the study through week 12 when serum calcium and 25(OH)D levels will be measured at the end of the study. The study will continue until participants have been followed for 12 weeks.

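### The participant stopping limits carry the wrong units: calcium is in meq/L in all three statements, and 25(OH)D is in ng/dl in one of them

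*Combined protocol and SAP*

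**What the plan says.** The combined protocol and SAP states the individual stopping rule in three places.

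- **Study Intervention, item 1.** Both supplements stop if calcium is at or above 10.6 "meq/L and/or a 25(OH)D level" at or above 80 "ng/dl at the 6 week visit". No symptom trigger is given here.
- **G6, a. Safety Monitoring.** The calcium limit is again 10.6 meq/L. The 25(OH)D limit is 80 "ng/ml or symptoms of vitamin D intoxication (e.g. bone pain, nausea, vomiting) will stop treatment".
- **Stopping plans.** The calcium limit is again 10.6 meq/L. The 25(OH)D limit is 80 "ng/ml or symptoms of vitamin D intoxication (e.g. bone pain, nausea or vomiting) will stop treatment".

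The eligibility criteria show the units the protocol otherwise works in. Exclusion criterion 5 bars fasting serum calcium at or above "10.2 mg/dl at the screening visit". Inclusion criterion 4 requires total 25(OH)D below "20 ng/ml (50 nmol/L" in the alternative unit). Nothing in the text explains a change of units between eligibility and stopping.

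**The concern.** The calcium number looks like a mg/dl value, since it sits just above the 10.2 mg/dl screening limit, but it carries a unit in which it means about twice as much. The 25(OH)D limit under Study Intervention uses a unit 100 times smaller than the one used everywhere else. The two errors pull in opposite directions: one limit would hardly ever act, the other would almost always act.

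This matters because these are the only numeric limits for taking a participant off treatment, and tolerability is a stated purpose of the pilot: "we will determine the tolerability of taking 5,000 IU of Cholecalciferol with 1000 mg elemental calcium daily for 12 weeks". Week 6 is also the only scheduled laboratory check at which the rule can change exposure, because supplementation ends at week 12. Stopped participants stay in follow-up without supplements, so a misapplied rule would also affect the adherence and change-over-time results in the Analysis Plan.

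**Working it through.** The plan gives no calculation behind the stopping limits, so there is no figure of its own to reproduce on this point. The check is a unit conversion.

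**Inputs from the document**
- Calcium stopping limit: 10.6 meq/L (all three statements).
- 25(OH)D stopping limit: 80 ng/dl (Study Intervention); 80 ng/ml (Safety Monitoring and Stopping plans).
- Calcium exclusion limit at screening: 10.2 mg/dl (Exclusion criterion 5).
- 25(OH)D entry ceiling: 20 ng/ml = 50 nmol/L (Inclusion criterion 4).

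**Inputs not in the document (physical constants)**
- Calcium atomic mass 40.078, valence 2.

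**Calcium**
1. Conversion: mg/dl = meq/L × (atomic mass / valence) / 10 = meq/L × (40.078 / 2) / 10 = meq/L × 2.0039.
2. Limit as written: 10.6 × 2.0039 = 21.24 mg/dl. With the mass rounded to 40.0 it is 21.20, so rounding the constant does not matter.
3. Against the screening limit: 21.24 / 10.2 = 2.08.
4. Screening limit in meq/L: 10.2 / 2.0039 = 5.09.
5. Probable intent, 10.6 mg/dl, in meq/L: 10.6 / 2.0039 = 5.29. The written limit is 10.6 / 5.29 = 2.00 times that.
6. Rise needed by a participant who enters just below 10.2 mg/dl: 21.24 − 10.2 = 11.04 mg/dl as written, against 10.6 − 10.2 = 0.4 mg/dl under the probable intent.

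**25(OH)D**
1. Conversion: 1 ng/ml = 100 ng/dl.
2. Limit under Study Intervention: 80 / 100 = 0.8 ng/ml.
3. Against the other two statements: 80 / 0.8 = 100-fold lower.
4. Against the entry ceiling: 20 / 0.8 = 25-fold lower.
5. On the protocol's own scale of 50 / 20 = 2.5 nmol/L per ng/ml: 0.8 × 2.5 = 2 nmol/L, against 80 × 2.5 = 200 nmol/L.

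**Side by side**

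| Limit | As written | Same limit in the protocol's usual unit | Probable intent |
|---|---|---|---|
| Calcium, all three statements | 10.6 meq/L | 21.2 mg/dl | 10.6 mg/dl |
| 25(OH)D, Study Intervention | 80 ng/dl | 0.8 ng/ml | 80 ng/ml |
| 25(OH)D, the other two | 80 ng/ml | 80 ng/ml | 80 ng/ml |

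**The case against.** The strongest reply is that the intent is plain and staff would apply it correctly. The same outside laboratory measures serum calcium at screening, week 6 and week 12 under one assay description. Results will therefore probably arrive in the unit used for screening, and staff would compare a number near 10 with 10.6. Only someone who actively converted the units would go wrong. For 25(OH)D, the dedicated Stopping plans section already gives 80 ng/ml, and nobody is likely to stop a participant for excess vitamin D at a level below the deficiency ceiling for entry.

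There are other safeguards too. Staff ask about intoxication symptoms at weeks 6 and 12, and two of the three statements make symptoms a reason to stop. Participants receive their results and are told to share them with a physician. The protocol also says: "A data safety monitoring board will review all adverse events and laboratory data at 6 weeks to ensure safety of all participants". The laboratory rule can alter treatment at only one scheduled visit, in 15 participants.

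Much of this stands as a judgement of what would happen in practice. It lowers the likelihood of harm, and for 25(OH)D the document itself resolves the conflict two to one. It does not rescue the calcium limit. A workable value can only be inferred from a different criterion, the board review states no thresholds of its own, and a symptom trigger misses hypercalcaemia without symptoms, which is what a laboratory limit is for. The missing symptom trigger under Study Intervention is, fairly, a matter of harmonisation and not a contradiction.

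**Conclusion.** The concern holds. All three statements set the calcium stopping limit at a level equal to about 21.2 mg/dl, roughly twice both the entry limit and the probable intent. One of the three sets 25(OH)D 100-fold too low. The case for correction rests mainly on calcium, because no correct version exists anywhere in the document.

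This depends on three assumptions. First, strictly, the text shows only that value and unit do not fit; that the calcium unit is the wrong part is an inference, though a strong one, from the mg/dl screening limit. Second, the conclusion that the calcium limit would hardly ever act assumes a literal reading and that calcium will not double during the study. Third, the conclusion that nearly everyone would stop on 25(OH)D assumes a literal reading of Study Intervention and that participants taking 5,000 IU daily are above 0.8 ng/ml at week 6.

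The sample-size statement and its adverse-event detection probabilities are unaffected.

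**What to change.** Ask the clinical lead to confirm the intended limits, then make these changes:

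1. Change the calcium unit from meq/L to mg/dl under Study Intervention, Safety Monitoring and Stopping plans.
2. Change the 25(OH)D unit from ng/dl to ng/ml under Study Intervention.
3. Add the symptom trigger under Study Intervention so that the three statements agree.

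If the probable values are confirmed, each statement would stop both supplements at calcium of 10.6 mg/dl or more, at 25(OH)D of 80 ng/ml or more, or on symptoms of intoxication. Leave the 10.2 mg/dl exclusion limit as it is; it is a separate criterion.

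The cost is a short amendment with four unit corrections and one added phrase. Design, sample size, visits and assays stay the same.

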## Early withdrawal of subjects

A subject may withdraw from the study anytime he/she wishes. Any participant who withdraws from the study along with their reasons for withdrawing from the study will be reported to the Loyola Institutional Review Board.

## G2. Schedule of visits and measurements

If the subject meets all of the eligibility criteria after screening measures described above are completed, he/she will be consented by the research investigator or designee. Screening Visits/Baseline Visit:

	Prior to enrollment	+Enrollment Visit	Six weeks	12 weeks
Verify interest in study and eligibility	x	x		
Inclusion/exclusion form	x			
Obtain informed consent	x			
Obtain consent for biorepository	x			
Obtain HIPAA authorization for study (part of consent form)	x			
Measure sitting BP	x	x	x	x
Assess dietary calcium intake	x			
Measure serum calcium	x		x	x
Measure total 25(OH)D	x		x	x
Measure parathyroid hormone levels		x		x
Measure free 25(OH)D		x		x
Measure 1,25(OH) 2 D		x		x
Measure 24-hour urine calcium excretion	x			X

Pill counts			X	X
Adverse event check list			X	x

+All laboratory tests for the enrollment visit will be performed in blood collected during the screening visit to reduce participant burden. A fasting blood sample will be collected during the screening visit and any unused sample will be stored in a -80° freezer. All blood samples collected from persons who do not meet study eligibility will be discarded. Participants will be asked to provide written informed consent during the screening visit to allow their urine and serum specimens to be placed into the Loyola CRO biorepository.

Adverse event check list will be completed at six and twelve week visits by study investigators.

**Visit Frequency:**

Potential study eligibility will be determined at a screening visit. For those persons who meet study eligibility, an enrollment visit will be scheduled within 4 weeks of the screening visit. During the enrollment visit, participants will be provided the vitamin D and calcium supplements. Participants will return at 6 and 12 weeks for blood pressure measurement and for collection of a fasting serum specimen. A 24-hour urine collection will be obtained at the enrollment visit and at the week 12 visit.

**Study forms:**

- Consent form
- Inclusion/Exclusion Summary Form -completed by study staff
- Consent form for the biorepository
- Blood pressure form- enrollment visit, 6 and 12 week visits -completed by study staff
- Adverse event form-completed at 6 and 12 weeks
- Pill count form-completed at 6 and 12 weeks

**Measurements:**

- Seated Blood Pressure and Pulse
- Body mass index
- Fasting Serum calcium
- Fasting Serum creatinine
- 24-hour urine calcium
- Estimated calcium intake
- Total 25(OH)D level
- Free 25(OH)D level
- 1,25(OH)2D level
- Parathyroid hormone level

All study participants including participants who completed the screening visit but did not enroll in the study will be provided a copy of all their laboratory reports. This report will be in the form of a letter from [name] and will be sent directly to the study participants.

**G6. SAFETY AND ADVERSE EVENTS**

**a. Safety Monitoring**

We will query any hospitalizations or emergency room visits over the past month and reasons for those visits at the baseline, 6 and 12 week follow-up visits. Serum calcium and vitamin D levels will be measured at 6 and 12 weeks and anyone with serum calcium levels  $\geq 10.6$  meq/L and/or a 25(OH)D level  $\geq 80$  ng/ml or symptoms of vitamin D intoxication (e.g. bone pain, nausea, vomiting) will stop treatment. All adverse events will be reported to the Loyola University Chicago Health Sciences Institutional Review Board. The dose of vitamin D3

(5,000IU) is 1000 IU lower than the recommended dose for treating adults with 25(OH)D levels < 20 ng/ml. We will also exclude individuals with calcium intake that is at or above the current recommended daily calcium intake (1000 mg).

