Screening visits will occur in the CTRE clinic on the 1st floor and written informed consent for the screening visit and study will be obtained by research staff or investigators. At the screening visit, participants will provide written informed consent. Participants will also be asked to provide written informed consent for their serum and urine specimens to be placed in a biorepository for future studies. Participating in the biorepository is optional and will not affect their ability to participate in the screening exam or their overall eligibility to participate in the BBC and Vitamin D study. The screening visit will take ninety minutes to complete. Potential participants will be instructed to fast for at least four hours prior to the screening exam. All laboratory tests taken during the screening visit will be for research purposes and will not be part of standard care. During a screening visit, a research investigator will review the past medical history and any medication use to ensure the participant meets all inclusion and exclusion criteria. Resting blood pressure will be taken per protocol and height and weight will be measured. A fasting blood sample (15 ml) will be collected from the potential participant. Blood will be sent to Quest for measurement of serum creatinine and calcium and vitamin D. Participants will be asked to collect a 24-hour urine collection to measure urinary calcium excretion. Urine calcium will be measured by Quest. We anticipate that we will need to screen 60 adults to identify 15 individuals who are eligible for the study. Data collected from any individual who is found not be eligible for the study will be kept in a secure database (REDCAP) on a secure Loyola drive. For participants who do not enroll in the BBC and Vitamin D study, all banked specimens will be discarded unless they provided written informed consent to participate in Loyola's biorepository.

[figure not shown]

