Once the lab values for the potential participant have been reported to the investigators, then study eligibility may be determined. Individuals will be contacted by phone or via mailed letter regarding study eligibility. For those individuals who are eligible to participate in the study, an enrollment visit will be scheduled within 28 days of the screening visit. The enrollment visit and all subsequent visits will be held at Loyola University Chicago Health Sciences Campus in the CTRE clinic. In order to reduce participant burden, we will bank serum specimens from the screening visit. For those participants who provide written informed consent to enroll in the BBC and Vitamin D study, we will use this banked serum to measure 25(OH)D and 1,25(OH)2D using an LC/MS method at Quest. During the enrollment visit, participants will receive education about the study and the potential risks of participating and will provide written informed consent. The Loyola pharmacy will dispense the cholecalciferol and the calcium citrate to the enrolled participants.

Participants will then return at 6 and 12 weeks after the enrollment visit and participants will be instructed to fast at least four hours before the next visits. At the 6 and 12 week visit, a fasting blood specimen (15 ml) will be collected. Study staff will query participants about adverse effects and symptoms of vitamin D intoxication. Pill counts will be done at the 6 and 12 week visits. Participants will also collect their urine for 24 hours at the 12 week visit for measurement of urinary calcium excretion.

d. Randomization procedures-not applicable

This is a single arm non-blinded study.

Figure 1. Flowchart of study procedures

**e. Optional Biobanking.** Participants may *optionally* agree to reposit blood and urine samples into CRO-BIOREP (LU# 204853) for future research purposes. Participants will sign a second informed consent document should they agree to reposit their samples. The research team members and Biorepository staff will each retain a copy of the signed repository informed consent document. It is important to point out that participants do not need to agree to reposit samples in order to participate in the study.

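### No symptom checklist is scheduled before dosing, so this one-arm pilot's symptom count can include complaints already present at enrollment (minor: the hospital-care question looks back one month over six-week intervals)

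*Combined protocol and SAP*

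**What the plan says.** **Symptom and adverse event recording.** The table in G2 (Schedule of visits and measurements) marks the adverse event checklist in the six-week and 12-week columns only. The note below it agrees: "Adverse event check list will be completed at six and twelve week visits by study investigators". The Study forms list has the same timing: "Adverse event form-completed at 6 and 12 weeks". In VI. Study Procedures, the symptom query is described together with these two follow-up visits: "Study staff will query participants about adverse effects and symptoms of vitamin D intoxication". Under Visit Frequency, the supplements are handed out at the enrollment visit.

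**What is collected before dosing.** At screening, "a research investigator will review the past medical history and any medication use to ensure the participant meets all inclusion and exclusion criteria". The only other relevant item is the baseline use of the hospital-care question below.

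**Analysis.** VIII. Analysis Plan says that the number of participants with symptoms, and all adverse events, will be counted. It sets no new-onset condition and no comparison with baseline.

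**Hospital-care question.** Part a of G6 (Safety Monitoring) opens with this sentence: "We will query any hospitalizations or emergency room visits over the past month and reasons for those visits at the baseline, 6 and 12" (the last two being weeks of follow-up). On timing, VI. Study Procedures says "Participants will then return at 6 and 12 weeks after the enrollment visit", and Visit Frequency agrees: "Participants will return at 6 and 12 weeks for blood pressure measurement".

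**Oversight.** IV. Administrative Organization adds: "A data safety monitoring board will review all adverse events and laboratory data at 6 weeks to ensure safety of all participants".

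**The concern.** The Abstract says that the pilot will assess safety and feasibility, and the sample size section says that it will determine tolerability. (III. Study Aims does not list safety separately.) There is no control arm and no blinding. A record made before the first dose is therefore the main way to separate nausea or bone pain that a participant already had from symptoms that began on the supplements. Blood pressure, the laboratory measures and hospital care all have a baseline value in this plan. Symptoms do not.

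At stake is the tolerability figure that the larger trial would inherit. If complaints from before dosing enter the count, the regimen looks less tolerable than it is. A symptom record from before dosing cannot be reliably rebuilt afterwards.

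The second issue is smaller. A question limited to the past month, asked at visits six weeks apart, does not by itself reach back to the previous visit. The days left out include the first days on supplements.

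**Working it through.** **1. The plan's own safety figure.** Table 2 gives the probability of seeing at least one adverse event among n = 15. The formula is 1 − (1 − p)^15:
- p = 20%: 0.965 (stated 0.96)
- p = 10%: 0.794 (stated 0.79)
- p = 5%: 0.537 (stated 0.54)

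These reproduce and are not in dispute. The formula counts any participant who reports an event, whatever its cause or onset.

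**2. Is there a symptom record before dosing?** Setting the sections side by side:

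| Source | Timing | Content |
|---|---|---|
| Screening history review (VI.c) | before dosing | medical history and medication, to check eligibility |
| Hospital-care question (G6.a) | baseline, weeks 6 and 12 | hospitalizations and emergency visits |
| Symptom query (VI.c) | weeks 6 and 12 | adverse effects, symptoms of intoxication |
| Checklist (G2) and form (Study forms) | weeks 6 and 12 | adverse events |

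The first two rows are the only ones before dosing, and neither is described as a symptom record. Every scheduled symptom record falls after supplements have been dispensed.

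**3. Effect on the count.** A participant whose only reported symptom was present before dosing adds 1/15 = 6.7 percentage points to the proportion with symptoms. Two such participants add 2/15 = 13.3 points, and three add 3/15 = 20.0 points.

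The documents give no background rate. Purely as an illustration, assume that a symptom unrelated to the supplements has a prevalence of 5%, 10%, 20% or 30%. The expected number among 15 is then 0.75, 1.5, 3.0 or 4.5, and the probability that at least one participant reports it is 0.54, 0.79, 0.96 or 0.995. These prevalences are assumptions, not estimates for this population.

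**4. Look-back of the hospital-care question.** Inputs: visits at weeks 6 and 12, so two intervals of 42 days; treatment of 12 weeks, or 84 days; a look-back of one month, taken as m = 28 to 31 days. Days outside the question = 2 × (42 − m).

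| m | Per interval | Total | Share of 84 days |
|---|---|---|---|
| 31 | 11 | 22 | 26.2% |
| 30 | 12 | 24 | 28.6% |
| 28 | 14 | 28 | 33.3% |

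The uncovered days are the first 11 to 14 of each interval. This assumes visits exactly on schedule; late visits would widen the gap. A look-back to the previous visit leaves 0 of 84 days uncovered.

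**The case against.** **The checklist cannot be seen.** It is not reproduced and may record onset dates or whether a complaint was already present. That stands, so one cannot say that the symptom count has no baseline reference at all. But onset asked at week 6 rests on recall of up to six weeks, which is weaker than a record made before the first dose.

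**The text leans towards new events.** The symptom query concerns adverse effects and intoxication, and Stopping plans is worded for symptoms that arise during the study. Several conditions that could cause such symptoms are excluded at screening. This may reduce the problem, but the Analysis Plan carries no such limit into the count.

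**No consequence is shown.** The count is descriptive, no tolerability threshold depends on it, and over-counting is the cautious direction for safety. This stands and keeps the severity low.

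**Hospital care is covered by other routes.** The adverse-effect query and the checklist have no stated recall limit, all adverse events go to the ethics board, and the safety board reviews them at 6 weeks. A reader might infer that about a quarter to a third of hospitalizations would be missed. Another might scale down the Table 2 probability at a 20% rate from 0.965 to 0.883–0.909. Both readings require the dedicated question to be the only route of capture, and the documents describe others. The loss may be zero.

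**The remedy is partial.** Intermittent symptoms can still be misclassified, and without a control arm a new symptom cannot be attributed to the supplements. Both limits are real, but a partial separation is still better than none.

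**Conclusion.** The main point holds. The checklist and form are scheduled only after dosing starts, no symptom record before dosing is described, and the planned count is not restricted to new symptoms. The count can therefore be too high, by 6.7 percentage points for each participant whose only symptom predates dosing. How many such participants there would be cannot be derived from the documents. The conclusion assumes that the checklist does not already settle onset reliably, which cannot be checked.

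The look-back point holds only as a gap in one question: 22 to 28 of 84 days, for a 28- to 31-day month and visits on schedule. It does not show that events would be lost.

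Serum calcium, 25(OH)D and urine calcium are measured objectively and are untouched. A reader might also infer that the sample size statement or the rule for stopping treatment is at fault. Nothing here supports that: the n = 15 probabilities reproduce, and this point concerns what is recorded and counted. Overall severity is low.

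**What to change.** 1. **G2 and Study forms.** Complete the same adverse event checklist at the enrollment visit, before supplements are dispensed. Mark the Enrollment Visit column of the checklist row and add enrollment to the form line. State a look-back for this first completion, for example the past 6 weeks, so that it matches the follow-up intervals.
2. **VIII. Analysis Plan.** Report all symptoms and, separately, those not present at enrollment. Extend the second group to symptoms that have worsened only if the checklist grades severity; no section describes grading.
3. **G6, a. Safety Monitoring.** At weeks 6 and 12, ask about hospitalizations and emergency visits *since the last study visit*. Keep the one-month wording at baseline.

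The cost is a few extra minutes at a visit that already takes place and recall about two weeks longer (11 to 14 days) for the hospital-care question. No new visit, sample or participant is needed. No change to the rule for stopping treatment is proposed.
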